#### 2.5.4 Supportive analyses

Not applicable.

#### 2.6 Analysis of the key secondary objective

There is no key secondary objective.

## 2.7 Analysis of secondary objective(s)

The secondary objectives of this study are:

- To evaluate the systemic exposure of indacaterol resulting from single orally inhaled doses of QMF149 75/40 μg.
- To evaluate the safety and tolerability of QMF149 75/40 µg after single dose administration in pediatric patients.

#### 2.7.1 Secondary endpoints

#### Pharmacokinetics:

Systemic exposure of indacaterol after single dose administration of QMF149 75/40  $\mu$ g

**Safety parameters:** All safety data, including adverse events, laboratory measurements, vital signs, 12 Lead ECG

## 2.8 Safety analyses

For all safety analyses, the safety set will be used. All listings and tables will be presented by treatment group. Screen failure data will not be presented in the listings.

#### 2.8.1 Adverse events (AEs)

All information obtained on adverse events will be displayed by treatment sequence and patient.

All treatment emergent AEs will be summarized and listed.

AEs starting on or after the time of the first inhalation of study drug and until 30 days after the last inhalation will be classified as a treatment emergent AE. Any AEs that started during the study after signing informed consent and before the time of the first inhalation of study drug will be classified as a prior AE and will not be included in tabulations of the treatment emergent AEs.

The following treatment emergent AE summaries will be produced:

- by treatment, system organ class and preferred term,
- by treatment, system organ class, preferred term, and maximum severity

Novartis	Confidential	Page 14 of 16
SAP Amendment 1		Study No. CQMF149G2203

suspected drug-related AEs by system organ class and preferred term, SAEs by system organ class and preferred term, and AEs leading to discontinuation of study-drug by system organ class and preferred term.

The number and percentage of patients with the most frequent AEs will be summarized by treatment.

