6.1.5 Treatment duration

The planned treatment is 1 treatment, single dose each for MF 100 μ g TH and QMF149 75/40 μ g. For patients that discontinue from treatment, refer to Section 9.1.1.

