6.3.1 Participant numbering

Each patient is identified in the study by a Patient Number (Patient No.), that is assigned when the patient is enrolled for screening and is retained for the patient throughout his/her participation in the trial. A new Patient No. will be assigned at every subsequent enrollment if the patient is re-screened. The Patient No. consists of the Center Number (Center No.) (as assigned by Novartis to the investigative site) with a sequential Patient Number suffixed to it, so that each patient's participation is numbered uniquely across the entire database. Upon signing the informed consent form, the patient is assigned to the next sequential Patient No. available.

A new ICF/patient assent will need to be signed if the investigator chooses to re-screen the patient after a patient has screen failed, and the patient will be assigned a new Patient No.

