9.1.1 Study treatment discontinuation and study discontinuation

If the patient cannot properly and sufficiently inhale the dose of study medication at each treatment visit and if the patient does not provide a PK sample at each designated timepoint on both treatment days, the patient must be discontinued from the study.

Discontinuation of study treatment for a patient occurs when study drug is stopped earlier than the protocol planned duration, and can be initiated by the patient, patient's parent/legal guardian, or the investigator.

The investigator must discontinue study treatment for a given patient if, on balance, he/she believes that continuation would negatively impact the risk/benefit of trial participation.

Study treatment must be discontinued under the following circumstances:

- Patients who have not received or retained a full dose of study drug cannot be re-dosed during a study visit and should be discontinued
- Patient's or parent/legal guardian's wish including withdrawal of informed consent
- Administration of a prohibited medication
- ECGs:
 - At predose time on Day 6, if the absolute $QTcF \ge 450$ msec or an increase from baseline of > 60 msec on 2 adequate ECGs at least a minute apart and the physician interprets the data from ECG machine to not initiate study treatment.
 - 2nd or 3rd degree AV block
 - Atrial or ventricular arrhythmias (as judged clinically significant by the investigator)
- Any severe AE or SAE considered possibly related to the study medication
- Adverse events for which continuation of the study drug would be detrimental
- If a patient develops a medical condition that requires use of prohibited treatment as per Section 6.2.2, or if patient exhibits a behavior of non-compliance regarding prohibited medications.
- Pregnancy (see Section 10.1.4)
- Any situation in which study participation might result in a safety risk to the patient
- Clinically significant abnormal laboratory value(s) for children 6 to < 12 years, as per the discretion of the physician
- Any other protocol deviation that results in a significant risk to the patient's safety
- If the COVID 19 pandemic (or any other reason including any public health emergency) limits or prevents an on-site study visit(s), then such patients should be discontinued

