9.1.1.1 Replacement policy

Twenty-four (24) patients must complete the two (2) dosing PK collection study visits which includes all PK sampling timepoints. Dropouts and non-completers will be replaced as needed. Patients who have received a dose of study treatment and who drop-out or discontinue for any reason, may be re-screened after a minimum of 14 days.

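### Do the by-treatment adverse event tables need a written rule for assigning events to a dose and for counting children who re-enrol?

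*SAP*

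**What the plan says.** SAP 2.8.1, with the same text in Protocol 12.5.1, classes as treatment-emergent "AEs starting on or after the time of the first inhalation of study drug and until 30 days after the last inhalation". The system organ class and severity tables are split by treatment, and "The number and percentage of patients with the most frequent AEs will be summarized by treatment". A further summary covers "AEs leading to discontinuation of study-drug by system organ class and preferred term". That item does not itself mention treatment, but SAP 2.8 adds that "All listings and tables will be presented by treatment group".

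Protocol 6.1.4 gives every child MF Twisthaler on Day 1 and QMF149 on Day 6. Protocol 6.1.5 confirms that "The planned treatment is 1 treatment, single dose each", and Table 8-1 lets the Day 6 visit slip by up to three days. SAP 2.2 analyses patients by the treatment or treatments received. SAP 5.1.2 treats an event of uncertain timing as on-treatment and leaves the detailed date rules to the programming specification.

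On stopping, Protocol 9.1.1 says: "Discontinuation of study treatment for a patient occurs when study drug is stopped earlier than the protocol planned duration". On returning, Protocol 9.1.1.1 says that patients who have had a dose and "who drop-out or discontinue for any reason, may be re-screened after a minimum of 14 days". Protocol 6.3.1 adds: "A new Patient No. will be assigned at every subsequent enrollment if the patient is re-screened". The protocol glossary makes that number the patient's unique identifier.

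**The concern.** Three things look wrong at first sight.

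- **Assignment.** A single window covers both doses, yet the tables have a column for each treatment. SAP 2.2 works per patient, so it places a child in both columns without saying where that child's event goes.
- **Re-enrolment.** A child who is dosed, stops and returns has two numbers that neither document links. The child could be counted twice in the Safety Set. Because 14 days is shorter than the 30-day window, an event after the new QMF149 dose could also fall inside the window of the old number.
- **Discontinuation.** QMF149 is the last planned dose. If stopping means stopping early, little is left to stop once it has been inhaled. A zero in that column could then be read as good tolerability when it only reflects the dosing order.

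Safety and tolerability of QMF149 is a secondary objective, and descriptive tables are the whole of its analysis, so the counting rules deserve a look.

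**Working it through.** The plan states no figure for the AE tables. Its only related figure is enrolment in SAP 3, which reproduces: 24 / (1 − 0.25) = 32.

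**1. Does the assignment rule change the result that matters?**

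Inputs: doses 5 to 8 days apart (Protocol Table 8-1, Day 6 to Day 9) and 30 days of follow-up after the last dose (SAP 2.8.1). Assumptions: constant background rate, no drug effect, and 30-day incidence p = 10%, 20% or 30%, because the documents give no rate.

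Daily hazard h = −ln(1 − p)/30. For p = 20%, h = 0.2231/30 = 0.00744. With doses 5 days apart:

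- Most recent dose: MF Twisthaler 1 − exp(−5h) = 3.7%; QMF149 1 − exp(−30h) = 20.0%.
- Thirty days after each dose: 20.0% in both columns, with some events counted twice.
- Whole patient window in any column the child belongs to: 1 − exp(−35h) = 22.9%.

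The QMF149 column across the three rules, doses 5 to 8 days apart:

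| p | Most recent dose, or 30 days after each dose | Whole window |
|---|---|---|
| 10% | 10.0% | 11.6–12.5% |
| 20% | 20.0% | 22.9–24.6% |
| 30% | 30.0% | 34.0–36.4% |

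At p = 20% and 24 children, that is 4.8 children against 5.5 to 5.9. The column tied to an objective shifts by about one child. The MF Twisthaler column shifts far more, because the most-recent-dose rule gives it 5 to 8 days at risk against 30. Those unequal windows follow from the single-sequence design and would remain if the rule were written down.

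**2. Partial dates.** If Day 1 is uniform over a month of 30.44 days, both doses fall in the same month for (30.44 − 8)/30.44 = 74% to (30.44 − 5)/30.44 = 84% of children. This is the share of children for whom a month-only onset date would be ambiguous. It does not say how often such dates occur. AEs are asked about at the Day 6 visit, 5 to 8 days after Day 1, so month-only dates should be rare.

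**3. Re-enrolment.**

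- Shortest case: re-screened 14 days after stopping on Day 1 and dosed the next day. The new MF Twisthaler dose comes at 14 + 1 = 15 days and the new QMF149 dose at 20 to 23 days. Overlap with the old window is 30 − 15 = 15 days, of which 7 to 10 follow QMF149.
- If Exclusion 16 in Protocol 5.2 (no prescription drugs in the four weeks before initial dosing) covers the earlier study dose, the overlap is at most 30 − 28 = 2 days. None of it follows QMF149, since 28 + 5 = 33 > 30. Whether it applies is unclear: read literally, it also catches the inhaled steroid that Inclusion 4 requires.
- If k of the 8 planned non-completers return (k = 0 to 8, assumed) and 32 numbers are dosed in all, those numbers stand for 32 − k children. One event reads 1/32 = 3.1% instead of at most 1/24 = 4.2%.

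**4. Discontinuation.** The definition in Protocol 9.1.1 points to a count near zero after QMF149. The list of triggers in the same section points the other way. A severe or serious event possibly related to study medication, AV block and use of a prohibited medication are not limited to the time before the last dose. SAP 2.3.1 takes discontinuation from the disposition page. A site could therefore record an event after a full QMF149 dose as leading to discontinuation. A near-zero count is possible but not forced.

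**The case for a change.** The strongest argument for a change is that the rule is missing, costs one sentence, and alters printed numbers. SAP 5 says its appendix holds the programming rules for the analyses in Section 2, yet this rule is not there. The sponsor chose to let dosed children return, so the analysis should say how they are counted. And a near-zero discontinuation count on QMF149 could mislead a reader who does not think about the dosing order.

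Most of the facts in this stand; the consequence does not follow.

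- The omission is genuine, but in a fixed-order, two-dose study the most recent dose is the obvious rule. Dose times are recorded (Protocol 6.7.2), AEs are listed by patient, dosing is listed by patient, and listings carry the study day (SAP 2.1.1). A reader can check the placement of individual events.
- Double counting is the default outcome of the numbering rule only if nobody links the numbers. SAP 2.2 defines the Safety Set by patients, and no section says a returning child counts twice. For one event to appear under both numbers, the site would have to enter it twice. The 30-day follow-up under the old number makes that possible, but nothing asks for it.
- A footnote saying that an AE after a full QMF149 dose cannot lead to discontinuation could contradict the reported data, because the definition and the trigger list in Protocol 9.1.1 disagree and must first be reconciled. What stands is a point of interpretation: these counts should not be compared between treatments.

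**Conclusion.** No change to the plan follows. The missing assignment rule is a gap that analysts fill sensibly, in descriptive tables that test nothing. Under the assumed background rates, the choice of rule moves the QMF149 incidence by about 2 to 6 percentage points at most, and by nothing between the two more natural rules. The larger movement is in the MF Twisthaler column, which supports no objective. Writing down the most-recent-dose rule would give the tables analysts would produce anyway.

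The re-enrolment effect depends on an unknown number of returning children and on a 15-day overlap that is the extreme case. It could be 2 days or less if the four-week exclusion applies, and it is zero if re-dosing comes 30 or more days after the first dose. The discontinuation point is a caution for whoever reads the table. The primary comparison of mometasone exposure uses none of these counts.

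This rests on assumed constant background rates with no drug effect, on analysts using the most recent dose, and on a programming specification that is not among the documents and may already settle the date rules.

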Period Visit Name Days	Screening Screening -14 to -1	Treatment		Early Termination	Follow Up
		Day 1	Day 1 Day 6 1 6 -0 +3	-	Day 36 ¹ 36
		1			
Obtain parental Informed Consent / patient assent (if applicable)	Х				
Register Patient and Visit in IRT	Х	Х	Х		
Demography	Х				
Inclusion / Exclusion criteria ²	Х	Х			
Medical history/current medical conditions	Х				
Prior/ concomitant medication review	Х	Х	Х	Х	
AE/SAE	Х	Х	Х	Х	Х
Device training	Х	Х	Х		
Physical Examination	Х	Х	Х	Х	
Hematology	Х		Х	Х	
Clinical Chemistry	Х		Х	Х	
Urinalysis	Х		Х	Х	
Pregnancy and assessments of fertility ³	Х	Х	Х	Х	
Electrocardiogram (ECG)	Х		Х	Х	
Vital Signs	Х	Х	Х	Х	
Height and Weight	Х				
Telephone patient/parent/legal guardian in advance of study visit ⁴		х	х		
Dose administration		Х	Х		
PK blood collection		Х	Х		
Snack/Meal ⁵		Х	Х		
Safety Follow up Call					Х

Confidential

Novartis Clinical Trial Protocol (Version No. 01)

Page **35** of **63** Protocol No. CQMF149G2203

Period	I Screening	Treatment		Early Termination	Follow Up			
Visit Name	e Screening	Day 1	Day 6		Day 36 ¹			
Day	-14 to -1	1	6 -0 +3	-	36			
 ^X Assessment to be recorded in the clinical database or received electronically from a vendor ¹ This would occur 30 days after last study treatment. ² Inclusion/Exclusion evaluation at screening is recorded in CRF. Inclusion/Exclusion prior to dosing on Day 1 should be documented in source. ³ Serum pregnancy test at screening (approximately 0.5 mL blood volume) and urine pregnancy test during treatment visits ⁴ Patient/Parent/Legal Guardian should be reminded to withhold controller ICS on Days 1 and 6 study visits AND to withhold rescue medication within 8 hours of Days 1 and 6 study visits. ⁵ Patients should consume a small snack approximately 1 hour post-dose and a meal approximately 4 hours post-dose. Snack and meal times should be recorded on the CRF and food content should be recorded in source documentation. 								

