If discontinuation of study treatment occurs, the patient should NOT be considered withdrawn from the study. The patient should return to the clinic as soon as possible, after discontinuation of study drug, for a study treatment discontinuation visit (End of Treatment will act as an early discontinuation visit in this case) and directly move into the 30 day follow-up period. Early Termination visit assessments detailed in the Table 8-1 should be completed and recorded in

the eCRF. The investigator must determine the primary reason for the patient's premature discontinuation of study treatment and record this in the Study Disposition eCRF.

The data which must continue to be collected for all discontinued patients are adverse event and serious adverse events for up to 30 days after drug discontinuation until the end of the study follow-up visit. Documentation of attempts to contact the patient must be recorded in the source documentation.

If the patient fails to return for an end of study visit for unknown reasons, every effort should be made to contact them. For patients already started Day 1, the COVID 19 pandemic (or any other reason) may limit or prevent an on-site study visit(s). These patients should be discontinued and a phone or virtual visit will occur for safety monitoring and discussion of the participant's health status including 30 days safety follow-up. If patients cannot visit the site to have a urine pregnancy test done, the urine pregnancy test can be performed at home and the result reported to the site. If the patient can attend the early termination visit after Day 1, safety monitoring, discussion of the participant's health status, and urine pregnancy test (dipstick) should be performed as the early termination visit, then 30 days safety follow up will be performed.

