12.5.1 Safety endpoints

Adverse events

All information obtained on adverse events will be displayed by treatment sequence and patient.

All treatment emergent AEs will be summarized and listed.

AEs starting on or after the time of the first inhalation of study drug and until 30 days after the last inhalation will be classified as a treatment emergent AE. Any AEs that started during the study after signing informed consent and before the time of the first inhalation of study drug will be classified as a prior AE and will not be included in tabulations of the treatment emergent AEs.

The following treatment emergent AE summaries will be produced:

- by treatment, system organ class and preferred term,
- by treatment, system organ class, preferred term and maximum severity

suspected drug-related AEs by system organ class and preferred term, SAEs by system organ class and preferred term, and AEs leading to discontinuation of study-drug by system organ class and preferred term.

The number and percentage of patients with the most frequent AEs will be summarized by treatment.

Vital signs

All vital signs data will be listed by treatment sequence, patient, and visit/time and if ranges are available, abnormalities (and relevant orthostatic changes) will be flagged. Summary statistics will be provided by treatment and visit/time.

12-lead ECG

PR, QRS, QT, QTcF, and RR intervals will be obtained from 12-lead ECGs for each participant during the study. ECG data will be read and interpreted centrally. All ECG data will be listed by treatment sequence, patientand visit/time, abnormalities will be flagged. Summary statistics will be provided by treatment and visit/time.

Clinical laboratory evaluations

All laboratory data will be listed by treatment sequence, patient, and visit/time and if normal ranges are available abnormalities will be flagged. Summary statistics will be provided by treatment and visit/time.

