# 1.1 Study design

This is an open-label, two-period, single-sequence, crossover study to assess the pharmacokinetics, safety and tolerability of single inhaled doses of mometasone furoate (MF) when administered alone via MF Twisthaler® (TH) or as an indacaterol acetate/MF fixed dose combination (QMF149) via the Concept 1 (C1) device in  $\geq 6$  to <12 year old asthma patients. The study includes two open-label single-dose treatment visits. On the first treatment visit (Day 1) patients receive a single inhaled dose of 100 µg MF administered via the Twisthaler® device. On the second treatment visit (Day 6) patients receive a single inhaled dose of 75/40 µg indacaterol acetate/MF fixed dose combination (QMF149). Both treatments are in addition to their rescue medication and potentially SoC asthma therapy (excluding MF and indacaterol acetate).

Patients currently taking low-dose ICS asthma medications other than MF can enroll in the study. However, since the patients will be provided MF or QMF149 as part of study treatment on Day 1 and Day 6 respectively, patients should be instructed not to take low-dose ICS medication on the 2 treatment days.

The study will include the following:

- A screening period of up to 14 days
- Two single-dose treatment periods separated by a 4-7 day washout period (4 days is minimum washout)
- A 30-day investigational drug-free follow-up period

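### By-treatment AE percentages may set 5-8 days at risk after MF against 30 days after QMF149, because the SAP gives neither an attribution rule nor a common post-dose window

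*SAP*

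**What the plan says.** - **Order and timing.** MF Twisthaler is given on Day 1 to every child. SAP 1.1 continues: "On the second treatment visit (Day 6) patients receive a single inhaled dose of" the QMF149 combination. Protocol Table 8-1 allows Day 6 a window of -0 to +3 days.
- **Treatment-emergent window.** SAP 2.8.1 and protocol 12.5.1 define a single window for the whole study: any event that begins from the first inhalation onward and "until 30 days after the last inhalation will be classified as a treatment emergent AE". There is no separate end to the MF period.
- **Follow-up.** Footnote 1 to protocol Table 8-1 says of the Day 36 contact: "This would occur 30 days after last study treatment". For a child who discontinues, protocol 9.1.1 requires continued collection of "adverse event and serious adverse events for up to 30 days after drug discontinuation".
- **Tables.** Treatment-emergent AEs are summarised "by treatment, system organ class and preferred term" (protocol 12.5.1, repeated in SAP 2.8.1), and again with maximum severity. In addition, "The number and percentage of patients with the most frequent AEs will be summarized by treatment". SAP 2.8 says all safety tables are presented by treatment group.
- **What is absent.** Neither document says under which treatment an AE is counted once a child has had both doses. The treatment-received definition in SAP 2.2 and protocol 12.1 classifies patients, not events. SAP 5.1.2 decides only whether an AE with a partial date is on treatment at all. No common post-dose window and no rate per unit of time is planned.

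**The concern.** A crude percentage of children with an AE rises with the length of observation. In a single-sequence design whose AE window closes 30 days after the last dose, all of the long follow-up in a completer comes after the second treatment. If AEs are attributed to the most recent dose, ordinary childhood illness is collected for about a week under MF and for a month under QMF149, and the two percentages stand next to each other.

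Safety and tolerability of QMF149 is a secondary objective, MF is the only reference in these tables, and the interim look also draws on safety data. A reader could take a difference produced by observation time for a difference between products.

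**Working it through.** **1. Timing.** Both doses are single. From Day 1 to Day 6 is 6 - 1 = 5 days; to Day 9 it is 9 - 1 = 8 days. This agrees with the 4-7 day washout in SAP 1.1 if the dosing day is not counted. Follow-up after QMF149 is 30 days, and 6 + 30 = 36 reproduces the Day 36 contact. The planned numbers also reproduce: 24 / (1 - 0.25) = 32, so 8 dropouts are allowed for.

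**2. Time at risk under last-dose attribution, child taking both doses.** MF 5 to 8 days, QMF149 30 days. Ratio of time: 30/8 = 3.75 to 30/5 = 6.0.

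**3. Expected percentages with no drug effect.** The documents give no AE rate. Assume a constant rate r per child-day, equal in both periods, over the range 0.003 to 0.02. Then P(at least one AE in t days) = 1 - exp(-r t).

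| r per day | MF, 5 days | MF, 8 days | QMF149, 30 days | Ratio v 5 days | Ratio v 8 days |
|---|---|---|---|---|---|
| 0.003 | 1.5% | 2.4% | 8.6% | 5.8 | 3.6 |
| 0.01 | 4.9% | 7.7% | 25.9% | 5.3 | 3.4 |
| 0.02 | 9.5% | 14.8% | 45.1% | 4.7 | 3.05 |

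The range among completers is therefore about 3 to 5.8. At r = 0.01 and 24 completers, this is 24 x 0.049 = 1.2 to 24 x 0.077 = 1.8 children under MF against 24 x 0.259 = 6.2 under QMF149.

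**4. Children who stop after MF.** They stay in the safety set and add up to 30 days to MF. With d of 32 stopping, MF percentage = [(32 - d) x P(t) + d x P(30)] / 32; the QMF149 percentage is unchanged.

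- d = 4, r = 0.01, t = 5: (28 x 4.88% + 4 x 25.92%) / 32 = 7.5%; ratio 25.92 / 7.51 = 3.5. Over r = 0.003-0.02 and t = 5-8 days, the ratio is about 2.4 to 3.6.
- d = 8, r = 0.01, t = 5: (24 x 4.88% + 8 x 25.92%) / 32 = 10.1%; ratio 25.92 / 10.14 = 2.6. Over the same range, the ratio is about 2.0 to 2.6.

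**5. The other attribution rule.** If every AE within 30 days of a dose counts for that dose, both windows are 30 days and the no-effect ratio is about 1. In a child who takes both doses, however, 30 - 8 = 22 to 30 - 5 = 25 of MF's 30 days then fall after QMF149, and one AE can count under both treatments.

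**6. After the change.** With the same window after each dose, P(t) is the same in both columns and the no-effect ratio is 1.0. The same holds for a rate per child-day.

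**The case against.** The strongest reply is that the imbalance is inferred. The documents state no attribution rule, and the 5-8 against 30 days appears only if each AE goes to the most recent dose. That stands. It means the direction and size of the distortion cannot be read from the plan as fact. It does not remove the need for text, because the rule that equalises the windows mixes post-QMF149 time into MF.

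Second, the figure for completers alone is the extreme case, because children who stop after MF lengthen MF's observation. That stands too, and step 4 shows the dilution. Not every dropout need occur after the MF dose, so 8 of 32 is the other end of a range.

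Third, the background rate is assumed, and so is constant reporting. AEs are sought at the Day 1 and Day 6 visits and then at a follow-up call about 30 days after the last dose, so ascertainment may differ between the periods in a direction that is not known.

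Fourth, the stated safety objective evaluates QMF149 and names no comparison with MF. No AE test, margin or decision rule uses the contrast, and counts in 24 to 32 children are small. This limits the consequence to how a descriptive table is read. Small counts add noise but do not cancel a difference in observation time.

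A reader might also infer that early post-dose events would be lost among later background illness. The documents do not support that. AEs are displayed by patient, study day appears in the listings, and suspected drug-related AEs, SAEs and AEs leading to discontinuation have their own summaries. With so few children, early events can be read case by case.

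**Conclusion.** The point holds as a gap in the specification with a likely one-sided effect. Under last-dose attribution, a constant background rate of 0.003-0.02 per child-day and no drug effect, the expected QMF149/MF ratio of percentages is about 3 to 5.8 in completers and falls to about 2.0-2.6 if all 8 planned dropouts stop after MF and are followed for 30 days.

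A reader might go further and conclude that QMF149 will look several times worse. That is not supported: the attribution rule is unstated, the rate is assumed, and under a 30-days-per-dose rule the ratio is about 1. What can be said is that the side-by-side percentages may make QMF149 look worse by design, and that nothing in the plan prevents or flags it. The primary PK analysis is unaffected.

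**What to change.** In SAP 2.8.1 and protocol 12.5.1:

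- State the attribution rule, for example that an AE belongs to the last dose before its onset.
- Base the by-treatment percentages on the same window after each dose, with children given that treatment as the denominator. A window of 96 h is one example; it fits within the minimum washout of 4 days. Alternatively, add AEs per child-day at risk beside the crude percentages.
- Keep the full table up to 30 days after the last dose, labelled with the observation time for each treatment.

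The cost is SAP and protocol wording and one extra table from data already collected; no visits, samples or patients are added. The downside is that few events will fall in a short window: at the assumed 0.01 per day, 1 - exp(-0.01 x 4) = 3.9%, or about 0.9 of 24 children. MF events after 96 h would appear only in the full table and the listings.
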